Brain Imaging	See Note	See Note	See Section 9.1.1. Participants with a history of brain metastasis or symptoms should have surveillance MRI per standard of care (approximately every 12 weeks), or sooner if clinically indicated

Abbreviations:

Adverse Events; FU = Follow-up; NCI CTCAE = National Cancer Institute Common Terminology Criteria for Adverse Events; WOCBP = women of childbearing potential

^a Follow-up visits occur as follows: Follow-up Visit 1 = 30 days from the last dose (± 7 days) or coincide with the date of discontinuation (± 7 days) if date of discontinuation is greater than 42 days after last dose. Follow-up Visit 2 = 100 days (± 7 days) from last dose of study treatment. Participants must be followed for at least 100 days after last dose of study treatment. Both Follow-up visits should be conducted in person.

^b Survival follow-up visits may be conducted in clinic or by phone. The first survival follow-up visit will occur 3 months (± 14 Days) after Follow-up Visit 2, subsequent survival follow-up visits will occur every 3 months (± 14 days) thereafter. BMS may request that survival data be collected on all treated participants outside of the 3 month specified window. At the time of this request, each participant will be contacted to determine their survival status unless the participant has withdrawn consent for all contacts.

[figure not shown]

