Targeted Physical Examination	X	See note	To be performed within 72 hours prior to dosing on Days 1 and 22 of each cycle.
Vital Signs	X	See note	Including BP, heart rate, and temperature to be performed within 72 hours prior to dosing on Days 1 and 22 of each cycle.
Weight and ECOG Performance Status	X	See note	To be performed within 72 hours prior to dosing on Days 1 and 22 of each cycle. See protocol Appendix 6 for ECOG Performance Status scale.
Adverse Event Assessment	Continuously		Assessed using National Cancer Institute Common Terminology Criteria for Adverse Events (NCI CTCAE) v5.
Serious Adverse Event Assessment	Continuously		Assessed using NCI CTCAE v5.
Review of Concomitant Medications	Continuously		
Laboratory Tests	X	See note	To be performed within 72 hours prior to dosing on Days 1 and 22 of each cycle. Includes Hematology, Serum Chemistry, and Urinalysis as outlined in Table 9.4.4-1 . All labs should be checked prior to dosing.
Troponin	See note	See note	Q2W or Q3W monitoring (depending on selected chemotherapy regimen) for the first 12 weeks. For immunotherapy dosing visits, test should be performed and evaluated within 72 hours prior to immunotherapy dosing. Note: Symptom-based troponin testing may be performed as required.
Pregnancy Test (WOCBP only)	X	See note	Serum or urine (minimum sensitivity equivalent units 25 IU/L or equivalent units of HCG) within 24 hours prior to administration of first dose of study treatment and then every 4

Table 2-2: On-treatment Assessments - Participants Assigned to Investigator’s Choice XELOX or SOX (CA224060)

Procedure ^a	Cycle 1 Day 1 (Cycle = 6 weeks)	Other Time Points Relative to Dosing Schedule	Notes
			
weeks (± 7 days) regardless of dosing schedule. If collected with a dosing visit, then obtain within 24 hours prior to administration of study drug.
 
Home pregnancy test that meets the minimum sensitivity requirements can be used as necessary.

ECG	See note	See note	
Cycle 1: Performed within 72 hours prior to dosing on Day 1 and Day 22.
 
Cycles 2 to 4: Performed within 72 hours prior to dosing on Day 1.
 
Cycle 5 and Beyond: Performed within 72 hours prior to dosing every 12 weeks starting with C5D1.

Efficacy Assessments			
Body Imaging	See Note	See Section 9.1.1 . Tumor assessments should occur every 6 weeks (± 7 days) starting from randomization up to and including Week 48, then every 12 weeks (± 7 days) regardless of treatment schedule until BICR-confirmed disease	

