FOLFOX	X	See Note	First dose to be administered within 72 hours after randomization. FOLFOX dose schedule: see Table 7.1.3-1 . Subsequent FOLFOX doses may be administered within dosing windows per package insert or local standard.

Abbreviations: BP = blood pressure; C = cycle; D = day; ECG = electrocardiogram; ECOG = Eastern Cooperative Oncology Group; [REDACTED]
[REDACTED] FOLFOX = oxaliplatin, leucovorin, and fluorouracil; FU = Follow-up; HCG = human chorionic gonadotropin; IV = intravenous; NCI CTCAE = National Cancer Institute Common Terminology Criteria for Adverse Events; MRI = magnetic resonance imaging; [REDACTED]
[REDACTED] SAE = serious adverse event; concentration; [REDACTED] WOCBP = women of childbearing potential

^a If a dose is delayed, the procedures scheduled for that same time point should also be delayed to coincide with when that time point’s dosing actually occurs, except for body imaging, [REDACTED] and pregnancy testing.

Table 2-4: Follow-up Assessments - All Participants (CA224060)

Procedure	Follow-Up ^a Visits 1 and 2	Survival Follow-Up Visits ^b	Notes
Safety Assessments			
Targeted Physical Examination	X		Weight, BP, HR, and temperature. Targeted physical examination to be performed only as clinically indicated.
Serious Adverse Events Assessments	X		Assessed using NCI CTCAE v5
Adverse Events Assessment	X		Assessed using NCI CTCAE v5
Review of Subsequent Cancer Therapy	X	X	
Laboratory Tests	See Note		For Follow-up Visit 1, including Hematology, Serum Chemistry, and Urinalysis as outlined in Table 9.4.4-1 . Repeat at Follow-up Visit 2 if study treatment related toxicity persists.
Pregnancy Test (WOCBP only)	See Note		Serum or urine pregnancy testing is only required at FU1 and FU2 visits, unless increased frequency and duration is required per local regulations.

Table 2-4: Follow-up Assessments - All Participants (CA224060)

Procedure	Follow-Up ^a Visits 1 and 2	Survival Follow-Up Visits ^b	Notes
Efficacy Assessments			
Body imaging	See Note	See Note	See Section 9.1.1. For participants who discontinue study drug for reasons other than PD, follow-up scans should be performed every 6 weeks (± 7 days) up to and including Week 48, then every 12 weeks (± 7 days) until BICR confirmed PD, lost to follow-up, or withdrawal of consent. Radiographic assessments should be Q12W in Follow-Up and not be delayed until follow-up visits 1 & 2.

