5.1.3 Follow-up Phase

- The Follow-up Phase begins when the decision is made to discontinue a participant from study therapy.
- Follow-up Visit 1 will be performed 30 days from the last dose (± 7 days) or coincide with the date of discontinuation (± 7 days) if date of discontinuation is greater than 42 days after last dose. Follow-up Visit 2 will be performed 100 days (± 7 days) from last dose of study treatment. Participants must be followed for at least 100 days after last dose of study treatment. Both follow-up visits should be conducted in person.
- Survival visits - The first survival follow-up visit will be performed 3 months (± 14 days) after follow-up Visit 2. Subsequent survival follow-up visits will occur every 3 months (± 14 days) thereafter. Survival follow-up visits may be conducted in clinic or by phone.

Study follow-up assessment data are to be collected as outlined in [Table 2-4](#).

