9.1.4 BICR Confirmation of Progression

Sites should submit all scans to the imaging core lab on a rolling basis, preferably within 7 days of scan acquisition, throughout the duration of the study. BICR of scans will occur on a rolling basis, blinded to treatment arm, clinical data, and investigator assessment of submitted scans. When progression per RECIST 1.1 criteria is assessed by the investigator, the site will inform the imaging core lab, so that the BICR assessment of progression can be performed. The BICR review will be completed and the results provided to the site within 5 days of receipt of the scans, provided there are no pending imaging queries to the site.

Participants whose progression is not confirmed by the BICR will be required to continue tumor assessments (if clinically feasible) according to the protocol-specified schedule, or sooner if clinically indicated. Also, if participants discontinue treatment without radiographic progression, tumor assessments will continue according to the protocol specified schedule, as noted in [Section 2](#), until progression has been confirmed by BICR.

All study treatment decisions will be based on the investigator's assessment of tumor images and not on the BICR assessment. The BICR assessment of progression is only relevant for determining when tumor assessments for a given participant are no longer required to be submitted to the imaging vendor.

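### Before Week 48, Table 2-4 gives two incompatible scan intervals (6-weekly and 12-weekly) for participants who stop study therapy without progression

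*Protocol*

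**What the plan says.** The body-imaging row of protocol Table 2-4 covers participants who stop study drug for reasons other than progression. Its first sentence reads "follow-up scans should be performed every 6 weeks (± 7 days) up to and including Week 48, then every 12 weeks". The last sentence of the same cell reads "Radiographic assessments should be Q12W in Follow-Up and not be delayed until follow-up visits 1 & 2".

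Section 5.1.3 fixes when the second sentence starts to apply: "The Follow-up Phase begins when the decision is made to discontinue a participant from study therapy".

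The on-treatment tables set the calendar from randomization. Table 2-2 has "Tumor assessments should occur every 6 weeks (± 7 days) starting from randomization up to and including Week 48", followed by 12-weekly scans, and Table 2-3 says the same. Both tables make this independent of the treatment schedule and keep tumor assessments going after discontinuation without progression. Section 9.1.3 also has assessments continue per protocol when dosing is delayed or stopped. Section 9.1.4 says that "if participants discontinue treatment without radiographic progression, tumor assessments will continue according to the protocol specified schedule" and refers to Section 2 for the schedule.

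SAP 4.1.3 describes a different calendar: first scan at 12 weeks, then every 6 weeks up to 13 months, then every 12 weeks. It gives no separate off-treatment interval.

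**The concern.** A site cannot follow both sentences of the Table 2-4 cell for a participant who stops without progression before Week 48, and a monitor cannot judge a deviation against either. If the 12-weekly sentence is followed, how often a participant is assessed depends on whether treatment has stopped.

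Two kinds of endpoint are exposed. PFS and DOR take their progression and censoring dates from scans (SAP 4.1.2 and 4.1.3.1), so a sparser grid records progression later. The primary endpoint, ORR, needs confirmation at least 28 days after the first response (protocol 9.1.3, SAP 4.1.1), and the window for best response closes at progression or subsequent therapy. A responder who stops all therapy before the confirming scan could therefore be confirmed later, or not at all.

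**Working it through.** The plan gives no figure to reproduce. The check compares the two schedules and then sizes the difference.

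**1. Where the sentences conflict.** Before Week 48 the first sentence gives 6 weeks (42 days) and the last gives 12 weeks (84 days). After Week 48 both give 12 weeks. The conflict therefore covers only participants who stop without progression before Week 48.

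**2. Scans due to Week 48**, counting the 12 weeks from the last on-treatment scan (an assumption, because the sentence names no starting point):

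| Last on-treatment scan | 6-weekly sentence | 12-weekly sentence | Difference |
|---|---|---|---|
| Week 6 | 12, 18, 24, 30, 36, 42, 48 (7) | 18, 30, 42 (3) | 4 |
| Week 12 | 18, 24, 30, 36, 42, 48 (6) | 24, 36, 48 (3) | 3 |
| Week 18 | 24, 30, 36, 42, 48 (5) | 30, 42 (2) | 3 |
| Week 24 | 30, 36, 42, 48 (4) | 36, 48 (2) | 2 |

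**3. Delay in recorded progression.** If progression is uniform within an interval, the mean lag to the next scan is half the interval: 6/2 = 3 weeks against 12/2 = 6 weeks, a difference of 3 weeks.

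A simulation checked this. It used exponential progression times with medians of 4, 6, 8 and 10 months and 200,000 participants per scenario. Between 10% and 50% were set to stop after a last on-treatment scan drawn evenly from Weeks 6, 12, 18 and 24, and all of them then followed the 12-weekly sentence. The documents give neither the medians nor the shares; they are assumptions for scale.

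- Stopped without progression, then progressed before Week 48: recorded progression 3.3 to 3.5 weeks later.
- All participants: mean shift from 0.10 weeks (10% stopping, median 10 months) to 0.71 weeks (50% stopping, median 4 months).
- Recorded median PFS: unchanged at shares of 10% to 30%. At 50% it moved one 6-week step in two of four scenarios (18 to 24 weeks, and 36 to 42 weeks).

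**4. Response confirmation.** Both intervals exceed 28 days, so the confirmation rule itself is met either way; what changes is the date. A first response at Week 18 in a participant who then stops is confirmable at 18 + 6 = Week 24 or at 18 + 12 = Week 30. Protocol 10.1 and 10.3.9 time the ORR analysis to the Week 24 scan of the last participant randomized, so for the last entrants the later date could miss the cut.

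**5. SAP 4.1.3.** Using the SAP's own conversion, 13 months is 13 × 30.4375 / 7 = 56.5 weeks, against Week 48 in the protocol. The first scan is at Week 12, against Week 6. The SAP therefore cannot settle which Table 2-4 sentence applies.

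**The case against.** The strongest reply is that the documents mostly point one way. The 6-weekly sentence names the population, the window, the switch at Week 48 and the end point. Tables 2-2 and 2-3 and Section 9.1.3 agree with it. The last sentence may have been meant for the period after Week 48, or mainly to stop sites waiting for follow-up visits. This lowers the chance that many sites scan 12-weekly. It does not remove the conflict: the last sentence has no week limit, and the visits it mentions fall 30 and 100 days after the last dose, which suggests early follow-up. Section 9.1.4 does not decide the matter, because it only points back to Section 2.

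A reader might infer a sizeable loss of confirmed responses. With a constant hazard h = ln 2 / median PFS, the chance of an event before the next scan is 1 − exp(−h × t). At medians of 10 to 6 months this is 9% to 15% for t = 6 weeks and 17% to 27% for t = 12 weeks. The documents do not support using these figures here:

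- They give no median PFS, and a whole-population hazard is not the hazard of someone who has just responded.
- The group is unsized and narrow. It needs a response followed by stopping all study therapy before confirmation, whereas immunotherapy or chemotherapy may continue alone (protocol 5.1.2 and 7.3.1).
- Section 9.1.1 permits extra scans when clinically indicated and sends them to central review, so a 12-week wait is not forced.

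A reader might also infer bias between arms, since the trial is open-label. Nothing in the documents shows that stopping without progression, or the sentence sites follow, differs by arm.

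**Conclusion.** The contradiction is certain: one table cell gives two rules for the same participants, and no other section says which governs. It is confined to those who stop study therapy without progression before Week 48.

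If the 12-weekly sentence is followed, assessment frequency halves after stopping and progression is recorded about 3 weeks later in that subset. The overall effect on PFS is small, under one week on average even at an assumed 50% stopping. The effect on ORR is unquantified and limited to responders who stop all therapy before confirmation. The Week 24 against Week 30 example also assumes that the 12 weeks run from the last scan. A between-arm bias is possible only if such stopping, or site practice, differs by arm. The point is worth correcting because the wording is wrong as it stands and the repair is cheap, not because a large distortion has been shown.

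**What to change.** Delete the 12-weekly clause from the last sentence of the Table 2-4 body-imaging cell. State instead that, on or off treatment, scans stay on the single calendar of Tables 2-2 and 2-3 counted from randomization (every 6 weeks to Week 48, then every 12 weeks) and are not held back for follow-up visits 1 and 2. Correct SAP 4.1.3 to the same calendar; editing the protocol alone would leave the SAP in conflict with it.

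The cost is a short protocol clarification and a correction to the SAP text. No sample size, power or alpha figure changes. Where a site has been scanning 12-weekly, an affected participant would have about 3 more scans before Week 48 after a last on-treatment scan at Week 12 or 18 (4 after Week 6). Tables 2-2 and 2-3 and the first sentence of Table 2-4 already require all of these.

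The SAP's second version (July 2020) already writes of enrolment in the past tense, so the clarification may come too late for some participants. For them, a PFS and DOR sensitivity analysis that allows for interval censoring would show whether mixed intervals matter.

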3 INTRODUCTION

[figure not shown]
CA224060 is a Phase 2, randomized, open-label study of BMS-986213 (fixed-dose combination [FDC] relatlimab/nivolumab at a 1:3 ratio) in combination with investigator's choice chemotherapy, versus nivolumab in combination with investigator's choice chemotherapy, as first-line (1L) treatment in participants with untreated, unresectable, and either locally advanced or metastatic gastric cancer (GC) or gastroesophageal junction (GEJ) adenocarcinoma. Relatlimab is a fully human lymphocyte activation gene 3 (LAG-3) specific antibody that was isolated following immunization of transgenic mice expressing human immunoglobulin (Ig) genes. Relatlimab binds to LAG-3 with high affinity and inhibits binding of this receptor to cells bearing its ligand, major histocompatibility complex (MHC) Class II, the peptide antigen presentation molecule recognized by CD4+ T cells. Relatlimab binding inhibits the negative regulatory function of LAG-3 in vitro. By blocking the normal downregulatory pathway, relatlimab enhances the antitumor immune response and, thus, has the potential to inhibit the growth of multiple malignancies when administered in combination with other therapeutic immuno-oncology (IO) monoclonal antibodies (mAbs).

Nivolumab is a human mAb (IgG4-S228P) that targets the programmed death-1 (PD-1) cluster of differentiation 279 (CD279) cell surface membrane receptor. PD-1 is a negative regulatory molecule expressed by activated T and B lymphocytes.¹ Binding of PD-1 to its ligands, programmed death-ligands 1 (PD-L1) and 2 (PD-L2), results in the down-regulation of lymphocyte activation. Inhibition of the interaction between PD-1 and its ligands promotes immune responses and antigen-specific T-cell responses to both foreign antigens as well as self-antigens.

This Phase 2 study for BMS-986213 in GC and GEJ cancer will allow for direct comparison of the treatment effect of BMS-986213 in combination with investigator's choice chemotherapy, versus nivolumab in combination with investigator's choice chemotherapy, as measured by objective response rate (ORR) and duration of response (DOR) in participants with untreated, unresectable, and either locally advanced or metastatic GC or GEJ adenocarcinoma. The study will enroll patients with LAG-3 (+) and LAG-3 (-) expression status ($\geq 1\%$ or $< 1\%$; no indeterminate allowed).

[figure not shown]
[REDACTED] This clinical equipoise is further supported by the fact that the relationship between the immunogenic effects of chemotherapy and the clinical efficacy of immunotherapy has not been well characterized. Accordingly, participants will have their LAG-3 status ($\geq 1\%$ or $< 1\%$; no indeterminate allowed) determined prior to randomization, and enrollment into the 2 treatment arms for this study will be stratified based on LAG-3 expression status.

[figure not shown]

3.2.1 Research Hypothesis

In participants with untreated, unresectable, and either locally advanced or metastatic GC or GEJ adenocarcinoma, the administration of relatlimab plus nivolumab, in combination with chemotherapy, will improve ORR compared to nivolumab in combination with chemotherapy in the LAG-3 positive population.

[figure not shown]

[figure not shown]

3.3 Benefit-risk Assessment

Patients with advanced or metastatic GC and GEJ cancer present a significant unmet medical need.

[figure not shown]
The combination of relatlimab and nivolumab has been evaluated and appears to have a safety profile similar to nivolumab monotherapy. 

A pattern of immune-mediated adverse events (IMAEs) has been defined for treatment with nivolumab monotherapy and nivolumab in combination with other immune-targeting agents such as relatlimab. Management algorithms have been developed for these events and are provided in [Appendix 8](#). Most high-grade immune-related adverse events are manageable with the use of corticosteroids or hormone replacement therapy (endocrinopathies) as detailed in these algorithms.

Additional details on the safety profiles of relatlimab and nivolumab, including results from other clinical studies, are also available in the relatlimab, nivolumab, and BMS-986213 (relatlimab/nivolumab FDC) IBs.

The safety profile of nivolumab combined with oxaliplatin and fluoropyrimidine reflects the additive toxicity of nivolumab monotherapy and chemotherapy, and no new safety signal was identified. The ongoing internal and external studies of PD-L1 inhibitors in combination with chemotherapy in treatment-naïve advanced GC/GEJ participants suggest that this combination is tolerable and manageable, as no new safety signals have been detected.

To ensure an ongoing favorable risk/benefit assessment for participants enrolled in CA224060, an independent Data Monitoring Committee (DMC) will be utilized to evaluate the safety and efficacy of the treatments throughout the conduct of the trial.

This study involves investigational (relatlimab) and approved (nivolumab) drugs whose effects on pregnancy are not yet known or fully defined. Contraception is therefore required for participants who are women of childbearing potential (WOCBP), males, and for female partners of male participants who are WOCBP. These contraception guidelines (see [Appendix 4](#)) apply to all female participants and partners of male participants who could be exposed to the drug and who could become pregnant both during treatment and during a defined period after study drug treatment.

The combination of relatlimab and nivolumab, or nivolumab in combination with chemotherapy, has been tested in patients with GC, with promising preliminary data. [REDACTED]

4 OBJECTIVES AND ENDPOINTS

[figure not shown]
Table 4-1: Objectives and Endpoints

Objective	Endpoint
Primary	

 To compare ORR of BMS-986213 in combination with chemotherapy, with ORR of nivolumab in combination with chemotherapy, by BICR, in randomized participants with untreated, unresectable, and either locally advanced or metastatic LAG-3 positive GC or GEJ adenocarcinoma. 	
 ORR in participants who are LAG-3 positive. ORR is defined as the number of participants with a BOR of CR or PR divided by the number of randomized participants in each arm. BOR is defined as the best response designation as determined by the BICR, recorded between the date of randomization and the date of objectively documented progression (per Response Evaluation Criteria in Solid Tumors [RECIST 1.1]), death due to any cause, or the date of subsequent anticancer therapy, whichever occurs first.
Secondary	

 To assess the overall safety and tolerability of BMS-986213 in combination with chemotherapy vs. nivolumab in combination with chemotherapy in treated participants with advanced or metastatic GC or GEJ cancer. To compare ORR of BMS-986213 in combination with chemotherapy, with ORR of nivolumab in combination with chemotherapy, as assessed by investigator, in randomized participants with untreated, unresectable, and either locally advanced or metastatic LAG-3 positive GC or GEJ adenocarcinoma. To compare ORR by BICR and by investigator of BMS-986213 in combination with chemotherapy with ORR of nivolumab in combination with chemotherapy in randomized participants with advanced or metastatic LAG-3 negative GC or GEJ adenocarcinoma, and overall (across LAG-3 negative and positive groups). 	
 The incidence of AEs, SAEs, AE leading to discontinuation, deaths, and laboratory abnormalities in each arm. ORR is defined as above, as the number of participants with a BOR of CR or PR as assessed by the investigator using RECIST 1.1, divided by the number of randomized participants in each Treatment Arm. ORR in the LAG-3 negative group or overall is defined as above, as the number of participants in each population with a BOR of CR or PR divided by the number of randomized participants in each Treatment Arm, for that population.

Table 4-1: Objectives and Endpoints

Objective	Endpoint

 • To estimate DOR of BMS-986213 in combination with chemotherapy and DOR of nivolumab in combination with chemotherapy in randomized participants with advanced or metastatic LAG-3 positive GC or GEJ adenocarcinoma, by BICR and by the investigator. • To estimate DOR of BMS-986213 in combination with chemotherapy and DOR of nivolumab in combination with chemotherapy in randomized participants with advanced or metastatic LAG-3 negative GC or GEJ adenocarcinoma, and in the overall population by BICR and by the investigator. • To assess the difference in the overall survival (OS) of BMS-986213 in combination with chemotherapy and OS of nivolumab in combination with chemotherapy in randomized participants with untreated, unresectable, and either locally advanced or metastatic GC or GEJ adenocarcinoma separately in the LAG-3 positive and LAG-3 negative groups and overall. • To assess the difference in the PFS of BMS-986213 in combination with chemotherapy and PFS of nivolumab in combination with chemotherapy as assessed by BICR and investigator in randomized participants with untreated, unresectable, and either locally advanced or metastatic GC or GEJ adenocarcinoma separately in the LAG-3 positive and LAG-3 negative groups and overall. 	
 • DOR (based on BICR and investigator) is defined as the time between the date of first documented response (CR or PR) to the date of the first PD, per RECIST 1.1, death due to any cause, or the date of subsequent anticancer therapy whichever occurs first. • DOR in participants with advanced or metastatic LAG-3 negative GC or GEJ adenocarcinoma and for participants in the overall population (across the LAG-3 groups) is defined as above. • OS is defined as the time between the date of randomization and the date of death. For those without documentation of death, OS will be censored on the last date the participant was known to be alive. • PFS is defined as the time between the date of randomization and the date of the first documented PD per BICR or investigator or death due to any cause. Participants who die without a reported prior PD per BICR or investigator (and die without start of subsequent therapy) will be considered to have progressed on the date of death. Those who did not have documented PD per RECIST 1.1 criteria and who did not die, will be censored at the date of the last evaluable tumor assessment on or prior to initiation of subsequent anticancer therapy. Participants who did not have any on-study tumor assessments and did not die (or died after initiation of subsequent anticancer therapy) will be censored at the randomization date. Those who started any subsequent anticancer therapy without a prior reported PD will be censored at the last tumor assessment prior to or on the initiation of the subsequent anticancer therapy. Participants receiving treatment beyond progression must continue tumor assessments until such treatment has been discontinued.

Table 4-1: Objectives and Endpoints

Abbreviations: AE = adverse event; BICR = blinded independent central review; BOR = best overall response; CR = complete response;

[figure not shown]
[REDACTED] DOR = duration of response; [REDACTED]
[REDACTED] GC = gastric cancer; GEJ =
gastroesophageal junction; LAG-3 = lymphocyte activation gene 3; [REDACTED] ORR = objective
response rate; OS = overall survival; [REDACTED] PD = disease progression; PFS = progression-free
survival; [REDACTED] PR = partial response; [REDACTED]
[REDACTED] RECIST = Response
Evaluation Criteria in Solid Tumors; SAE = serious adverse event [REDACTED].

